2.1. Study Rationale

Protocol MEK-NF-201 is an open-label, multi-center, Phase 2b study being conducted to determine the efficacy and safety of mirdametinib (PD-0325901) in participants \geq 2 years old with symptomatic inoperable NF1-associated PNs. A Phase 2 study with PD-0325901 was previously conducted in NF1-associated plexiform neurofibromas (Weiss, 2017). This Phase 2, open-label study evaluated 19 participants (range 16 to 39 years) with symptomatic or progressing plexiform neurofibromas. Quantitative radiographic response in a target PN after administration of PD-0325901 at a dose 2 mg/m² BID (maximum dose of 4 mg BID) on a 3 weeks on/1 week off schedule was assessed. Overall, PD-0325901 was well tolerated; five subjects (26.3%) developed Grade 3 toxicities, with four of those subjects (21%) reporting a Grade 3 toxicity of pain. No subjects developed Grade 4 or higher toxicities and 1 subject experienced a SAE. This study demonstrated activity of PD-0325901 in subjects with a PN with eight participants (42.1%; 95% confidence interval [CI]: 20%, 67%) responding to PD-0325901 as defined by a \geq 20% reduction of the target PN after 1 year of therapy.

2.2. Background

To determine whether sustained Ras/Raf/MEK/ERK signaling contributes to neurofibroma growth, Jessen et al. conducted a study in a neurofibromatosis mouse model (Nf1_{fl/fl}; *Dhh-Cre*) with PD-0325901 (Jessen 2013). In this study, tumor bearing mice were randomly assigned to receive 10 mg/kg, 5 mg/kg or 1.5 mg/kg of either PD-0325901 or vehicle by oral gavage. All doses tested resulted in significant tumor volume reductions. A striking reduction in neurofibroma volumes was achieved after 60 days of PD-0325901 treatment. In all doses tested, PD-0325901 was well-tolerated with no apparent toxicity. Reduced tumor volume indicated that cell proliferation or cell death may be altered in neurofibromas. There was decreased cell proliferation observed at the end of treatment (60 days) as measured by reduction in the percentage of Ki67+ cells compared to controls.

A follow-up study utilizing the same Nf1_{fl/fl}; *Dhh-Cre* mouse model by Jousma and colleagues (Jousma, 2015) demonstrated that PD-0325901 at a dose of 0.5 mg/kg/day resulted in neurofibroma shrinkage and sustained inhibition of pERK equivalent to the 1.5 mg/kg/day dose. In this study, mice were exposed at the age of 1 month in some experiments with no apparent toxicities. The dose of 0.5 mg/kg/day used in this murine study is approximately equivalent to a dose of 2.5 mg twice daily (BID) in humans. These data are supportive of the use of low dose treatment with PD-0325901 for volume reduction of neurofibromas and are congruous with the

clinical dosing strategy used in the Weiss et al. (Section 2.1) study and the proposed Phase 2b study.

A detailed description of the chemistry, pharmacology, efficacy, and safety of mirdametinib (PD-0325901) is provided in the Investigator's Brochure.

2.3. Benefit/Risk Assessment

To date, the safety profile of single-agent mirdametinib (PD-0325901) in patients with advanced cancer (doses < 10 mg BID, intermittent schedule) has been characterized by mostly manageable and reversible toxicities. The most frequently reported adverse events have been rash, nausea, vomiting, diarrhea, and fatigue. The majority of the events were mild-to-moderate intensity. Other events that have been reported in lesser frequency include ocular disorders (visual disturbances, blurred vision, retinal vein occlusion), nervous system disorders (including confusion, slowed ideation, slurred speech, and hallucinations), musculoskeletal and connective tissue disorders (general weakness as well as neck muscle weakness associated with mild and moderate elevations in creatine kinase [CK]), and cardiac disorders (decreased left ventricular ejection fraction [LVEF], congestive heart failure). These events primarily occurred in patients receiving doses ≥ 10 mg (up to 30 mg) BID.

In order to minimize potential risk during study participation, participants will be carefully monitored for the development of toxicities throughout the study and guidelines for dose modification/discontinuation for selected adverse events are provided.

Based on the available nonclinical and clinical trial data, the benefit-risk balance is considered favorable for further development in patients with NF.

More detailed information about the known and expected benefits and risks and reasonably expected adverse events of mirdametinib (PD-0325901) may be found in the Investigator's Brochure.

3. Objectives and Endpoints

Table 1 Study Objectives and Endpoints

Objectives	Endpoints
Primary	
To evaluate the confirmed complete and partial response (PR) rate of mirdametinib (PD-0325901) using volumetric magnetic resonance imaging (MRI) analysis in participants with an inoperable NF1-associated PN that is causing significant morbidity.	Objective response rate at the end of the Treatment Phase (defined as PN decrease ≥ 20% compared to Baseline) using centrally read MRI volumetric analysis.
Secondary	
To evaluate the safety and tolerability of mirdametinib (PD-0325901) in participants with NF1 and symptomatic inoperable PN as measured by the incidence of adverse events (AEs);	Safety endpoints will include incidence of treatment-emergent adverse events, changes in laboratory parameters, vital signs, physical examination findings, and electrocardiograms (ECGs);
	Tolerability will be assessed according to toxicities graded by National Cancer Institute (NCI) Common Terminology Criteria for Adverse Events (CTCAE) Version (v) 5.0;
To determine the duration of response;	Duration of response for participants whose best response is complete response (CR) or PR using centrally read MRI volumetric analysis;
To evaluate the effect of mirdametinib (PD-0325901) on quality of life as measured by patient-reported outcomes (PROs); and	Change from Baseline in quality of life (QoL) assessed by the age specific Pediatric Quality of Life Inventory (PedsQL); and
To evaluate the effect of mirdametinib (PD-0325901) on pain as measured by patient-reported outcomes.	Change from Baseline in pain (assessed using the Numeric Rating Scale-11 [NRS-11] and Pain Interference Index [PII]) in the Treatment Phase.

Tertiary/Exploratory				
To evaluate the effect of mirdametinib (PD-0325901) on physical functioning as measured by PROs;	Change from Baseline in physical function status (Patient-Reported Outcomes Measurement Information System [PROMIS] – Physical Function/Mobility/Upper Extremity Scale) in the Treatment Phase;			
To determine Baseline functional impairments secondary to PN, and the effect of mirdametinib (PD-0325901) on functional outcomes depending on PN location;	Change in localized strength (dynamometer and Medical Research Council Muscle Scale), range of motion, and endurance (6-minute walk test) of PN associated functional impairment in the Treatment Phase;			
To determine time to progression (TTP) and progression free survival (PFS) in progressive PN;	TTP and PFS in progressive PN (≥ 20% increase in PN volume within 12 months prior to first dose of study treatment) using centrally read MRI volumetric analysis;			
To assess TTP of mirdametinib (PD-0325901) versus historical controls;	Time until Progressive Disease (defined as PN increase ≥ 20% compared to Baseline) using centrally read MRI volumetric analysis;			
To evaluate the effect of mirdametinib (PD-0325901) on PN associated disfigurement;	Change from Baseline in PN-associated disfigurement using standardized photography;			
To correlate MRI responses with Pharmacodynamic (PD) biomarkers in PN biopsies obtained pre- and post-treatment with mirdametinib (PD-0325901);	Change in levels of pERK and other applicable biomarkers in tumor biopsies at Baseline and Cycle 24 / Early Termination (ET) visit; and			
To evaluate the acceptability of the dispersible tablet formulation of mirdametinib (PD-0325901).	Summarize separately by self-report and the caregiver.			

4. Study Design

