 - **22a. Pediatric Oral Medicines Acceptability Questionnaire (P-OMAQ)** (Section 8.1.2.7): All participants that are utilizing the dispersible tablet (pediatric formulation) dosage form will complete the P-OMAQ (paper) self-report and caregivers will complete an observer report, as applicable. This assessment will only be completed once during the study.

23. Study treatment (Section 6):

- 23a. Study treatment assignment and first dose: After all study entry criteria (Sections 5.1 and 5.2) have been met and all Baseline pre-dose assessments have been conducted (SoA footnote 3), study treatment will be assigned using the interactive response technology (IRT) and first dose of study treatment will be administered followed by a 2-hour observation period.
- 23b. Dispensing: Study treatment will be dispensed to participants using the IRT every 2 Cycles at scheduled study visits (as described in the SoA). Cycle 24 Day 21 dispensing for 4 cycles will only occur if participant is continuing to LTFU Phase.
- 23c. Administration: Following the first dose (Cycle 1 Day 1), participants will self-administer study treatment orally on a twice daily (BID) dosing schedule of 2 mg/m² dose with a maximum dose of 4 mg BID. Dosing will be on a 28-day Cycle (4-week course) with a 3 week on/1 week off schedule.
- 23d. Diary/Accountability: Participants will record their daily dosing administration of each study treatment dose in the home ePRO device (provided by the Sponsor). Accountability will be performed by the Site personnel coinciding with each dispensing visit and recorded in the electronic case report form (eCRF).
- 24. Monthly wellness check-in (Section 8.2.10): Monthly telephone or email contact is required throughout the study (may be replaced by a face-to-face interaction when study visits occur, and the information can be obtained during the visit).
- 25. Concomitant medications will be collected starting at the time of informed consent/assent to 30 days after the last dose of study treatment. Refer to Section 6.5.2 for prohibited or restricted medications.
- 26. Adverse events (AEs) and Serious Adverse Events (SAEs), which may include clinical laboratory test variables, will be monitored and documented from the time of informed consent/assent to 30 days after the last dose of study treatment. Refer to Section 8.3 for more detail.

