- 27. Early Termination (ET) visit is applicable if a participant discontinues study treatment early for any reason during the study and participant should be encouraged to return to the Site to complete this visit as soon as possible. The ET visit should be conducted as close to the last dose of study treatment as possible and every effort should be made to complete all procedures.
- 28. Safety Follow-Up (SFU) visit is required to be conducted 30 days (+5 days) after the last dose of study treatment. This visit is not required for participants who are continuing study treatment in the Long-Term Follow-up Phase at Cycle 24 (End of Treatment Phase).

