6.6. Dose Modification

Every effort should be made to administer study treatment at 2 mg/m² BID; however, in the event of significant toxicity, dosing must be interrupted and/or dose reduced as described in Table 4 and Table 5.

Interruption of study treatment should continue until the toxicity is resolved to \leq Grade 1 or Baseline. An interruption of study treatment for more than 14 days due to any toxicity may require permanent discontinuation. After 14 days of interruption, study treatment may be resumed only after discussion with the Medical Monitor and approval by the Sponsor. Refer to Section 10.10.3 for the Medical Monitor contact details.

After interruption, study treatment may be resumed at a reduced dose as described in Table 4 and Table 5. Should the same Grade toxicity recur at the reduced dose and the AE is considered related to the study treatment, the participant may be discontinued at the discretion of the Investigator, pursuant to discussion with the Medical Monitor and Sponsor. Following a dose reduction, an increase in the study treatment dose due to a BSA change is permitted at the discretion of the Investigator with approval from the Medical Monitor and Sponsor.

An unscheduled visit may be performed at any time during the study. Assessments to be performed at the visit will be determined by the Investigator.

Table 4 Criteria For Dose Modification For Study Drug Related Adverse Events

RELATED ADVERSE EVENTS	INTERVENTION
OCULAR/VISUAL	
Any Grade ≤ 2 event.	Continue dosing and perform ophthalmologic exams every 2 to 4 weeks until resolution to Grade ≤ 1 or baseline.
Any Grade ≥ 3 event except RVO.	Interrupt dosing; if resolution to Grade ≤ 1 or baseline occurs within 14 days, re-start study treatment at the next lower dose following Table 5. Consider ophthalmologic exams every 2 to 4 weeks.
Grade ≥ 3 retinal vein occlusion (RVO)	Permanently discontinue study treatment
NEUROLOGICAL	
Grade ≤ 2 events such as hallucination, confusion or delirium lasting more than 24 hours AND after ruling out other possible causes.	Interrupt dosing; if resolution to Grade ≤ 1 or baseline occurs within 14 days, re-start study treatment at the next lower dose following Table 5.
Any Grade ≥ 3 event.	Withhold dose and discuss with the Medical Monitor. Consider permanent discontinuation after re-evaluating the benefit risk of ongoing study drug treatment
MUSCULOSKELETAL	

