7.1. Discontinuation of Study Treatment

It may be necessary for a participant to permanently discontinue study treatment prematurely or for the Sponsor to suspend study enrollment.

Participants who permanently discontinue from the Treatment Phase prior to the Cycle 24 visit will be required to return to the clinic for an early termination (ET) visit as close as possible to the last dose of study treatment (PD-0325901, mirdametinib). Participant will also be required to return for a Safety Follow-Up visit (30 days [+5 days] after the last dose of study drug) (refer to the SoA in Section 1.3 for timing and a complete list of required assessments to be conducted).

Conditions upon which the Sponsor will suspend additional enrollment in the study are described in the specified stopping criteria in Section 10.1.7.

Reasons for discontinuation of study treatment early may include:

[figure not shown]
- Participants who meet the definition of progressive disease (a ≥ 20% increase in the volume of the target PN as compared to the Treatment Phase Baseline [Section 10.7], confirmed by central radiologic review);
- Occurrence of any medical condition or circumstance that exposes the participant to substantial risk and/or does not allow the participant to adhere to the requirements of the protocol.
- Any SAE (refer to Section 10.3.2 for SAE criteria), clinically significant AE (refer to QTc stopping criteria below; Section 7.1.2), severe laboratory abnormality (refer to liver chemistry stopping criteria below; Section 7.1.1), intercurrent illness, RVO, or other medical condition which indicates to the Investigator that continued participation is not in the best interest of the participant;
- Pregnancy (refer to Sections 8.3.6 and 10.4 for additional details);
- Requirement of prohibited concomitant medication (Section 6.5.2);
- Participant failure to comply with protocol requirements or study-related procedures; or
- Termination of the study by the Sponsor as described in Section 10.1.7, the IRB or the regulatory authority.

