Cycle 24 Day 21 (End of Treatment Phase Visit)

Participants will not take their planned morning dose the day of the study visit. Instead they will take their morning dose of study treatment following the pre-dose PK blood draw (Section 10.8).

The PII and NRS-11 questionnaires will be completed using the home ePRO device daily for 6 consecutive days prior to the scheduled Cycle 24 Day 21 visit. At the Cycle 24 Day 21 visit, all PRO assessments (PedsQL [paper], PII, NRS-11, PROMIS, PGIS and PGIC [Table 9]) will

be completed prior to all other study assessments to minimize participant bias in the clinic. If the participant is utilizing the dispersible tablet (pediatric formulation) dosage form and has not yet completed the P-OMAQ (paper), they should complete the assessment at this visit. This assessment should only be completed once during the study.

Tumor volume will be measured by MRI (no contrast required) and scans to be submitted for central radiologic review (Section 8.1.1). Scan must precede the target PN biopsy. If sedation is used, sedation must be administered after the strength, range of motion, and 6-minute walk assessments if assessments are to be completed on the same day.

Tumor biopsy will be collected from the target PN (Section 8.1.6), if applicable.

Bone plate radiographs for participants 2 to 17 years of age, if applicable. (Section 8.2.9)

All previously dispensed study treatment will be collected for accountability.

LTFU Participants Only: Dispense 4 cycles of study treatment

Refer to the SoA (Section 1.3) for all additional procedures required at Cycle 24 Day 21.

Early Termination (ET) Visit

Participants that permanently discontinue study treatment early will be required to return to the clinic for an ET visit as close to the last dose of study treatment as possible.

At the ET visit, all PRO assessments (PedsQL [paper], PII, NRS-11, PROMIS, PGIS and PGIC [Table 9]) will be completed prior to all other study assessments to minimize participant bias in the clinic. If the participant is utilizing the dispersible tablet (pediatric formulation) dosage form and has not yet completed the P-OMAQ (paper), they should complete the assessment at this visit. This assessment should only be completed once during the study.

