Participants who complete Cycle 24 of the Treatment Phase and did not meet withdrawal criteria detailed in the protocol are eligible to participate in the LTFU Phase. Eligible participants will continue taking the last dose assigned in the Treatment Phase (approximately 2 mg/m² BID [maximum dose of 4 mg BID]) of mirdametinib, on an intermittent (3 weeks on/1 week off) dosing schedule in 28-day cycles. Participants will remain in the LTFU Phase until a withdrawal criterion is met as described in Section 7 of the protocol or mirdametinib is commercially available.

A participant is considered to have completed the Treatment Phase if he/she has completed the Cycle 24 visit (End of Treatment Phase) or has entered the LTFU Phase.

The treatment group labels that will be used in all outputs are presented in Table 2.

Table 2: Study Treatments

Actual Treatment	Treatment Label
PD-0325901 (approximately 2 mg/m ² BID)	Mirdametinib

Table 3 and Table 4 present the visit labels that will be used in all outputs for the Treatment and LTFU Phases, respectively.

Table 3: Study Visits – Treatment Phase

Visit	Visit Label
Screening	Screening
Cycle 1 – Week 1 (Baseline, study visit day 1)	C1D1
Cycle 1 - Week 3 (Cycle Day 15)	C1D15
Cycle 2 – Week 7 (Cycle Day 15)	C2D15
Cycle 3 – Week 11 (Cycle Day 15)	C3D15
Cycle 4 - Week 15 (Cycle Day 15)	C4D15
Cycle 5 – Week 19 (Cycle Day 15)	C5D15
Cycle 6 – Week 23 (Cycle Day 15)	C6D15
Cycle 7 - Week 27 (Cycle Day 15)	C7D15
Cycle 9 – Week 35 (Cycle Day 15)	C9D15
Cycle 11 – Week 43 (Cycle Day 15)	C11D15
Cycle 13 - Week 51 (Cycle Day 15)	C13D15
Cycle 15 – Week 59 (Cycle Day 15)	C15D15
Cycle 17 – Week 67 (Cycle Day 15)	C17D15
Cycle 19 – Week 75 (Cycle Day 15)	C19D15
Cycle 21 – Week 83 (Cycle Day 15)	C21D15
Cycle 23 – Week 91 (Cycle Day 15)	C23D15
Cycle 24 (End of Treatment Phase) - Week 96 (Cycle Day 21)	C24D21
Early Termination	ET
Safety Follow-up – 30 days after last dose	SFU

Document: S:\Q_146\Q_03974\MEK-NF-201\Prog_Stat\Documentation\SAP\MEK-NF-201 SAP v1.0.0.docx

Author:

Table 4: Study Visits - Long-Term Follow-up Phase

Visit	Visit Label
Cycle 28 (Cycle Day 15)	C28D15
Cycle 32 (Cycle Day 15)	C32D15
Cycle 36 (Cycle Day 15)	C36D15
Cycle XX (Cycle Day 15)	CXXD151
End of Treatment	EOT
Safety Follow-up = 30 days after last dose	LTSFU

¹The Long-Term Follow-up phase lasts an indefinite amount of time; visits will occur on day 15 of every 4th cycle with the cycle number inserted into this visit label format.

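### The Cycle 24 window lets the only scheduled post-baseline biopsy and its PK sample fall in the drug-free week, and Early Termination biopsies have no stated limit after the last dose, so the exploratory pERK–MRI correlation can be biased

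*Protocol*

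**What the plan says.** **Endpoint.** Protocol Section 3, Table 1 (Tertiary/Exploratory) sets out "Change in levels of pERK and other applicable biomarkers in tumor biopsies at Baseline and Cycle 24 / Early Termination (ET) visit". The objective is to correlate MRI responses with biomarkers in biopsies taken before and after treatment. SAP Table 1 repeats this and refers the details to a separate analysis plan. Study biopsies are for participants aged 18 or over (Section 8.1.6).

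**Dosing.** SoA footnote 23c: "Dosing will be on a 28-day Cycle (4-week course) with a 3 week on/1 week off schedule".

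**Cycle 24.** The Treatment Phase SoA (Section 1.3) gives this visit as Day 21 with a window of ±5 days. Table 7 says of it, "Tumor biopsy will be collected from the target PN (Section 8.1.6), if applicable", and, on dosing, "Instead they will take their morning dose of study treatment following the pre-dose PK blood draw". Table 7 also requires the MRI to come before the biopsy. Appendix 8 lists the PK sample and the biopsy at Cycle 24, Day 21, timepoint 0. SAP Table 3 labels the visit "Cycle 24 (End of Treatment Phase) - Week 96 (Cycle Day 21").

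**Early Termination.** SoA footnote 27: "The ET visit should be conducted as close to the last dose of study treatment as possible". Sections 7.1 and 7.2 and Table 7 say much the same. None gives a number of days. Appendix 8 gives the ET biopsy no day or timepoint and schedules no PK sample at ET.

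**Interruptions.** Section 6.6: "An interruption of study treatment for more than 14 days due to any toxicity may require permanent discontinuation". Section 7.1 lists among the reasons for stopping early: "Participants who meet the definition of progressive disease".

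**The concern.** Section 8.6 presents pERK as a marker of drug effect, and Section 4.3 uses its suppression on drug to support the dose. A biopsy taken some days after the last dose may show recovery of the pathway instead of the inhibition reached during treatment. Each adult has one scheduled post-baseline biopsy, so an off-drug value cannot be replaced by another.

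The two routes off drug act differently. Visits by completers that drift into the drug-free week add variation unrelated to MRI response, which weakens the correlation. ET biopsies are different because MRI progression is itself a reason for stopping. ET status can then link time off drug to a poor MRI outcome, which can create or inflate a correlation.

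There is also a plain inconsistency. On Cycle Days 22–26 no dose is scheduled, so a pre-dose draw followed by a morning dose has no meaning under the stated schedule. SoA Section 1.3 (visit window and footnote 23c), Table 7 and Appendix 8 must be reconciled.

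**Working it through.** **1. Reproduce the plan's visit day.** Study day = (cycle − 1) × 28 + cycle day. For Cycle 24 Day 21: 23 × 28 + 21 = 665, which matches SAP Table 12.

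**2. Window against schedule.** Dosing days are 3 × 7 = 21, so Days 1–21. The window is 21 − 5 = 16 to 21 + 5 = 26, which is 11 days (study days 660–670). Days 22–26 are drug-free: 5 of 11 (45%). Other on-treatment visits after Baseline are Day 15 ±2 or ±5 and end by Day 20, so only Cycle 24 crosses over.

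**3. Week label.** 665 / 7 = 95, so Day 21 is the last day of Week 95. Week 96 covers study days 666–672, or Cycle Days 22–28. The label may simply count 24 × 4 = 96 weeks, but read literally it points into the drug-free week.

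**4. Size, completers only.** The documents give no pERK recovery time, so these inputs are assumptions: on-drug suppression with mean 60% (Section 4.3 cites at least 60%) and SD 15 points, true correlation with MRI shrinkage 0.50, visits uniform over the 11 days, and recovery with half-time h. With t days off drug, measured suppression is s × w, where w = 2^(−t/h). For w independent of s and of shrinkage,

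r = 0.50 × 15 × E[w] / √(E[w²] × (60² + 15²) − E[w]² × 60²).

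For h = 1 day: E[w] = (6 + 0.5 + 0.25 + 0.125 + 0.0625 + 0.03125) / 11 = 0.6335 and E[w²] = 0.5757. The root is √(0.5757 × 3825 − 0.6335² × 3600) ≈ 27.5, and r = 7.5 × 0.6335 / 27.5 ≈ 0.17.

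**5. Size, ET.** By simulation under the same assumptions: 20% are ET cases, all with the worst MRI outcomes, biopsied uniformly 0–14 days after the last dose. In one run all others are biopsied on drug; in the other they are spread over the Cycle 24 window.

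| Recovery half-time | Suppression left at Day 26 | r, completers over window | r, ET off drug, others on drug | r, both together |
|---|---|---|---|---|
| 1 day | 2% | 0.17 | 0.73 | about 0.4 |
| 3 days | 19% | 0.29 | 0.71 | about 0.5 |
| 7 days | 37% | 0.42 | 0.68 | about 0.6 |
| 14 days | 47% | 0.47 | 0.64 | about 0.6 |

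The true value is 0.50 throughout. The bias can go down or up, and the two routes can partly cancel.

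**The case against.** The strongest defence is that the plan does place the biopsy on drug. Appendix 8 puts it at Day 21, timepoint 0, and Table 7 has a dose taken at that visit. This stands: the fault is a window looser than the intent. It would be wrong to say the protocol never ties the biopsy to a dosing day.

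A reader might infer that 45% of Cycle 24 biopsies will be off drug. The documents do not support that. Five of 11 counts permitted days, not expected visits, and sites may keep close to Day 21. With doses about 12 hours apart, a biopsy on the morning of Day 22 could also be only about 12 hours after the last dose.

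A reader might also infer that the correlation is distorted, or that the biopsies cannot answer the question. That goes too far. Section 4.3 reports suppression on drug and says nothing about recovery; if recovery takes weeks, the loss in completers is small. Appendix 8 requires dosing times to be captured, so time since last dose could be used in the analysis. The separate plan, which is not among these documents, may already do so. Other biomarkers are measured as well.

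The ET instruction is real and repeated, but it is not a limit. It also cannot shorten an interruption that came before the decision to stop. Analysis can set aside or model an off-drug biopsy, but it cannot recover the on-drug value. That much of the point survives.

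**Conclusion.** The point holds as a timing defect with a possible, unquantified bias. Three things are certain from the text: 5 of the 11 permitted Cycle 24 days are drug-free, the dosing instruction in Table 7 cannot apply on those days, and the ET biopsy has no numeric limit after the last dose.

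The effect on the correlation is conditional. It rests on pERK recovering within days, on how many biopsies actually fall off drug, and on how ET relates to MRI outcome. Under the stated assumptions a true r of 0.50 could appear as anything from about 0.17 to about 0.73; the completers-only effect shrinks to 0.47 at a 14-day half-time.

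The reach is narrow: one exploratory analysis in the adult cohort of about 50. Objective response rate and the secondary endpoints are unaffected. The change is still worth making, because the biopsy is invasive, is scheduled only once after Baseline, and can be protected by wording.

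**What to change.** 1. **SoA Section 1.3 and Appendix 8.** Set the Cycle 24 biopsy and PK window to −5/+0 days (Days 16–21), with the Cycle 24 MRI on or before the biopsy day so that the scan-first rule in Table 7 is kept. Other Cycle 24 assessments may stay at ±5. Reconcile the visit window, footnote 23c, Table 7 and Appendix 8.
2. **Early Termination.** Keep collecting these biopsies. Dropping those taken after a short cut-off would remove participants in a way related to outcome. Record the time from last dose to biopsy for every biopsy.
3. **Pharmacodynamic analysis plan.** Base the main pERK change and MRI correlation on biopsies taken while on drug, using a maximum time since last dose fixed in advance. Report off-drug and ET biopsies separately by time since last dose. If Cycle 24 collection is already complete, this step alone still applies.

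**Cost.** The biopsy scheduling window narrows from 11 days to 6 and the MRI must fit with it. The main pharmacodynamic analysis set becomes slightly smaller. No procedure is added.
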